## **9.7                    Data Analysis**

Descriptive analyses will be performed to gain an understanding of the qualitative and quantitative nature of the data collected and the characteristics of the sample studied. Continuous variables will be described with the following measures of central tendency and dispersion: the number of patients, missing observations, mean, standard deviation, median, interquartile range, minimum,

---

and maximum. Frequency, percentage, and number of missing observations will be provided for categorical variables. Exact Clopper-Pearson 95% CIs will be included where appropriate. The Kaplan-Meier method will be used for the analysis of time to event objectives.

In general, descriptive statistics of quantitative parameters (results and change from baseline) will be provided for observed cases, that is, patients having non-missing assessments at a specific timepoint. Missing data count will be presented.

All AE verbatim terms and medical history terms will be recorded and coded using the MedDRA. All previous and concomitant medication being recorded will be coded using World Health Organization Drug Dictionary (WHO-DD).

Baseline data will be defined as the data collected at the index date.

Computations and generation of tables, listings, and data for figures will be performed using statistical analysis system (SAS)® version 9.4 or higher (SAS Institute, Cary, NC, USA).

The full analysis will be described in a written and approved Integrated Analysis Plan (IAP).

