### **9.7.2 Derived and Transformed Data**

Primary and secondary effectiveness outcomes will be derived as per definition reported in [Section 9.1.2](#).

For OS, PFS, PFS2 and DoR, the percentage of patients alive at the time of outcome assessment (12 or 24 months) will be calculated as per the Kaplan-Meier approach.

For PFS, PFS2 and DoR, a patient progressing after stopping current treatment and starting a new therapy will be censored at the latest tumor assessment showing no progression before changing therapy.

For safety, time to onset of AE will be calculated as difference in days between start date of AE and the index date +1, while duration of AE (applicable for resolved AEs only) will be calculated as difference in days between end date of AE and start date of AE +1.

Time to Avelumab plus Axitinib discontinuation will be derived as difference in days between last dose of Avelumab plus Axitinib and the index date +1 and time to second-line therapy after study treatment discontinuation will be calculated as difference in days between start date of second-line treatment and last dose of Avelumab plus Axitinib +1.

As per NCCN-FACT Fksi-19 scoring guidelines (version 2), the total HRQoL score (range 0-76) will be calculated as sum of single items scores multiplied by 19 and divided by the number of items completed. NCCN-FACT Fksi-19 will also cover 4 subscales: DRS-P (items from 1 to 11, range 0-48), DRS-E (item 12, range 0-4), TSE (items from 13 to 15, range 0-12) and FWB (items from 16 to 19, range 0-12). The higher the subscores or the total score, the better the HRQoL. The subscales will be evaluable, if at least 50% of respective items will be answered and will be calculated as sum of items included in the subscale, multiplied by the item included in the subscale, and divided by the item answered in the subscale. The Fksi-19 questionnaire as a whole will be evaluable, if all subscales will be evaluable and at least 80% of all items will be answered. Score of items 11 (C6), 12 (GF5), and from 16 to 19 (GF1, GF3 and GF7) will be reversed before calculating total and subscale scores.

Every effort will be made to capture all available data by:

- Ensuring that primary variables of interest are those that are routinely collected as part of routine clinical practice and are available via medical charts, physician, and/or patient/caregiver reporting, as appropriate

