Time to onset and duration of AEs, time to Avelumab plus Axitinib therapy discontinuation, and time to second-line therapy after study treatment discontinuation will be summarized by descriptive statistics for continuous variables.

Type of therapy for management of related AEs and type of second-line therapy and third-line therapy will be presented according to the WHO-DD, considering the first digit of the ATC classification system (anatomic category) and the first 3 digits of the ATC class (therapeutic category).

Descriptive statistics will also be provided on body weight over the course of the study.

The scores (total and subscales) of the HRQoL at the index date and at every third cycle of Avelumab treatment (intervals of about 6 weeks) will be summarized using descriptive statistics for continuous variables. Possible trend in HRQoL will be also analyzed by repeated measure analysis.

[figure not shown]

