To analyze the nature, severity, duration, frequency, and timing of Adverse Events (AEs) that occurred from the index date up to 90 days post discontinuation of Avelumab plus Axitinib or completion of the 24 months (ie, end of the study) follow-up from the index date, whichever occurs first	Endpoint: Frequency and nature of all-cause AEs according to Medical Dictionary for Regulatory Activities (MedDRA) system organ class (SOC) and preferred term (PT) that occurred from the index date up to 90 days post discontinuation of Avelumab plus Axitinib or completion of the 24 months (ie, end of the study) follow-up from the index date, whichever occurs first.	15.1.1
To assess time to therapy discontinuation due to AE \geq Grade 3	Endpoint: Duration of Avelumab plus Axitinib therapy among patients who discontinued the study drugs due to all-cause AEs \geq Grade 3.	15.1.2
To assess therapy modifications due to AE related to Avelumab plus Axitinib therapy and management of AE related to Avelumab plus Axitinib therapy	Endpoint: Percentage of patients with therapy modifications due to AE related to Avelumab plus Axitinib therapy (eg, therapy interruptions and reductions of infusion rate for Avelumab, therapy interruptions, and dose reductions for Axitinib).	15.1
To determine percentage of patients receiving later-line therapy and frequency distribution of later-line therapy regimes among patients progressing on Avelumab plus Axitinib	Endpoint: Percentage of patients receiving later-line therapy and frequency distribution of later-line therapy regimes among patients progressing on Avelumab plus Axitinib including the names of medications of monotherapy/combination treatment used in second-line and third-line therapy.	15.1
To assess time to second-line therapy initiation (T2LT)	Endpoint: Time interval from Avelumab plus Axitinib therapy discontinuation to the initiation of second-line therapy.	14.2
To assess patient-reported potential signs and symptoms of immune-related AEs	Endpoint: Frequency of patient-reported signs and symptoms of potential immune-related AEs. Immune-related AEs may include immune-mediated pneumonitis, immune-mediated colitis, immune-mediated hepatitis, immune-mediated endocrinopathies, immune-mediated nephritis with renal dysfunction.	15.2.3

6 Overview of Planned Analyses

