UNK		<= Index date (month and year)	Before index date	Previous
UNK		<= Index date (month and year)	After index date	Previous and concomitant
UNK		> Index date (month and year) and <= last Avelumab/Axitinib (whichever comes later) [+ 30] days (month and year)	After index date	Concomitant
		<= Index date (date)	Before index date	Previous
		<= Index date (date)	After index date	Previous and concomitant
		> Index date (date) and <= last Avelumab/Axitinib (whichever comes later) [+ 30] days (date)	After index date	Concomitant

UNK = Unknown

Dates of study treatment	
 No imputation will be done for start date (index date will be present for all patients). 
End date of study treatments:
 
 In case the last date of study drugs is missing or incomplete the date of last administration of study drugs will be taken from the treatment termination eCRF pages.
--------------------------	---

	
 • If the last date of study drugs is completely missing and there is no EOT eCRF page and no death date the participant should be considered to be ongoing and use the cut-off date for the analysis as the last dosing date. • If the last date of study drugs is completely or partially missing and there is EITHER an EOT eCRF page or a death date available (within the cut-off date) then imputed last dose date is: 
 = 31DECYYYY, if only Year is available and Year < Year of min (EOT date, death date) = Last day of the month, if both Year and Month are available and Year = Year of min (EOT date, death date) and Month < the month of min (EOT date, death date) = min (EOT date, death date), for all other cases
Death date	
For survival analyses partially missing death dates will be imputed as follows:
 
If only the day is missing, the death date will be imputed to the maximum of the (non-imputed) day after the date of last contact and the 15th day of the month.
 
Otherwise it will not be imputed.

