	
DoR (months) = [date of event or censoring–date of first CR or PR +1]/30.4375
 
DoR will be estimated by the KM method. The percentage of censored patients will also be reported. Median event time will be reported, along with 25th and 75th percentiles. Percentage of patients experiencing event or being event-free at applicable timepoints will also be reported along with the corresponding two-sided 95% CIs.

Table 6 **Outcome and event dates for DoR**

Scenario	Date of event/censoring	Outcome
PD before subsequent anti-cancer therapy	Date of PD	Event
PD after subsequent anti-cancer therapy	Date of last adequate tumor assessment ^a documenting no PD before subsequent anti-cancer therapy is given	Censored
No PD/Death	Date of last adequate tumor assessment ^a documenting no PD/Death before subsequent anti-cancer therapy is given	Censored
Treatment discontinuation due to 'Disease progression' without documented progression	Not applicable	Information is ignored. Outcome is derived based on documented progression only.
Study end for consent withdrawn without PD	Date of last adequate tumor assessment ^a documenting no PD before subsequent anti-cancer therapy is given	Censored
Study end for lost to follow-up without PD	Date of last adequate tumor assessment ^a documenting no PD before subsequent anti-cancer therapy is given	Censored

^a If there are no adequate post-baseline assessments prior to the PD, then the time without adequate assessment should be measured from the index date; if the criteria were met the censoring will be on the index date.

T2LT

T2LT is defined as the time from the last dose of Avelumab plus Axitinib to the start date of second-line treatment for RCC.

	T2LT time (in months) = (Second-line treatment start date – last dose of Avelumab plus Axitinib + 1)/ 30.4375 (months)
--	--

	T2LT will be summarized by descriptive statistics for continuous variables.
--	---

The subgroup analyses will be performed on selected secondary endpoints (OS, DCR, PFS, and PFS2) based on the analysis set for all subgroup levels defined in [Section 8.2](#) “Subgroup definition and parametrization”. All the subgroup analyses are exploratory and will be performed unstratified.

No adjustment for multiplicity will be performed. In the case of a low number of participants within a category of the analysis set, the categories will be pooled when meaningful (see [Section 8.2](#)).

15 Safety Analyses

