Time to onset and duration of AEs, time to Avelumab plus Axitinib therapy discontinuation will be summarized by descriptive statistics for continuous variables.

Type of therapy for management of related AEs and type of second-line therapy and third-line therapy will be presented according to the WHO-DD, considering the first digit of the ATC classification system (anatomic category) and the first 3 digits of the ATC class (therapeutic category).

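### Time to second-line therapy is summarized only in patients who start it, with no rule for death or censoring, so the reported time runs short and moves with follow-up; time to treatment discontinuation has a related gap

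*SAP*

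**What the plan says.** Protocol 8.2 and SAP 5 list time to second-line therapy initiation as a secondary objective. SAP 14.2 gives the derivation: "T2LT is defined as the time from the last dose of Avelumab plus Axitinib to the start date of second-line treatment for RCC". The analysis is one sentence: "T2LT will be summarized by descriptive statistics for continuous variables". Nothing states what happens to a patient who stops treatment and dies before second line, or who has not started it by cut-off. In the same section PFS, PFS2 and DoR each get Kaplan-Meier estimation and a table of event and censoring dates.

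SAP 15.1.1 treats related variables the same way: "Time to onset and duration of AEs, time to Avelumab plus Axitinib therapy discontinuation will be summarized by descriptive statistics for continuous variables". For a patient with no last-dose date, no end-of-treatment page and no death date, SAP 9.9 says to treat the patient as ongoing and "use the cut-off date for the analysis as the last dosing date".

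The general rules point elsewhere. Protocol 9.7 states: "The Kaplan-Meier method will be used for the analysis of time to event objectives". SAP 9 says time-to-event data are summarized both descriptively and by Kaplan-Meier. Yet protocol 9.7.3, naming AE onset and duration, time to discontinuation and time to second line, says these "will be summarized by descriptive statistics for continuous variables".

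SAP 6.1 has the primary analysis report secondary endpoints limited to the first 12 months of observation, and the SAP 18 output list for that analysis includes a T2LT table.

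**The concern.** T2LT is a right-censored time with death as a competing event. Its formula cannot be evaluated without a second-line start date, so only starters contribute. Within fixed follow-up from the index date, a patient who stops treatment late can contribute only a short T2LT, and patients with a long wait are the ones most likely to be missing. The summary is then shorter than the time among starters with complete follow-up, and shorter again than the time by which a given share of all discontinuers has started.

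Because the size of this effect depends on follow-up, T2LT could be reported once at the 12-month analysis and again at the end with different values and no change in practice behind the difference.

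For time to discontinuation the text does not say whether patients still on treatment are in the summary. If they enter at cut-off as completed times, the mean is too low, and with only 12 months of data the median cannot exceed 12 months.

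**Working it through.** The plan states no expected value for either time, so there is no figure to reproduce. What follows is illustration under stated assumptions, with all times exponential.

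**T2LT: inputs**
- Time to discontinuation: median 13.3 months, borrowing the updated overall-population PFS median in protocol 7 as a stand-in. Hazard θ = ln 2/13.3 = 0.0521 per month.
- Second-line start after stopping: median 3 months (assumed). λ = ln 2/3 = 0.2311.
- Death after stopping: μ = 0.03 or 0.06 per month (assumed).
- Follow-up τ = 24 months (protocol 9.1.1) or 12 months (SAP 6.1).

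**T2LT: formulas**
- Density of an observed T2LT of length u, up to a constant: e^(-(λ+μ)u) × [1 − e^(-θ(τ−u))], for 0 < u < τ. Its median is the starters-only median.
- Starters-only median with unlimited follow-up: ln 2/(λ+μ).
- Time to 50% cumulative incidence among all discontinuers: −ln[1 − 0.5(λ+μ)/λ]/(λ+μ).

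For μ = 0.03: λ+μ = 0.2611, ln 2/0.2611 = 2.66, and −ln(1 − 0.565)/0.2611 = 3.19. For μ = 0.06: λ+μ = 0.2911, giving 2.38 and −ln(1 − 0.630)/0.2911 = 3.41. The truncated medians come from numerical integration of the density.

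| Quantity | μ = 0.03 | μ = 0.06 |
|---|---|---|
| Starters-only median, 12 months (months) | 1.89 | 1.76 |
| Starters-only median, 24 months (months) | 2.37 | 2.16 |
| Starters-only median, unlimited (months) | 2.66 | 2.38 |
| Time to 50% cumulative incidence (months) | 3.19 | 3.41 |
| Discontinuers contributing, 12 months | 65% | 61% |
| Discontinuers contributing, 24 months | 80% | 72% |

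Splitting the 24-month gap:
- Total gap to 50% cumulative incidence: 3.19 − 2.37 = 0.82, and 3.41 − 2.16 = 1.25 months.
- Due to truncation: 2.66 − 2.37 = 0.29, and 2.38 − 2.16 = 0.22 months. The rest comes from moving from starters to all discontinuers.
- At 12 months truncation costs more: 2.66 − 1.89 = 0.77, and 2.38 − 1.76 = 0.62 months.

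The size is sensitive to the assumed T2LT median. At 1.5 months the smallest total 24-month gap is 1.54 − 1.34 = 0.20; at 6 months the largest is 8.12 − 3.24 = 4.88. The direction is the same throughout.

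**Time to discontinuation, ongoing patients entered at cut-off**
- True mean: 1/θ = 19.2 months. Mean with cut-off taken as complete: (1 − e^(-θτ))/θ, which is 0.714 × 19.19 = 13.7 at 24 months and 0.465 × 19.19 = 8.9 at 12 months.
- Median: the smaller of 13.3 and τ. At 24 months it is 13.3, correct. At 12 months it is 12.0, where Kaplan-Meier would report it as not reached.

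**The case against.** Much of the other side stands, and it rules out several stronger readings.

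- **The SAP departs from the protocol.** A reader might infer this from protocol 9.7. But protocol 9.7.3 prescribes the same descriptive summaries and the SAP follows it. One can also read SAP 9 as adding Kaplan-Meier on top of the descriptive statistics in 14.2 and 15.1.1. The conflict is between general and specific text inside each document, and it still needs resolving because neither gives T2LT a censoring rule.
- **Time to discontinuation is computed only in patients who stopped.** Under the assumptions above that would give medians of 8.5 months at 24 months and 5.1 at 12. No passage says ongoing patients are excluded, and SAP 9.9 can keep them in. Those figures do not follow from the text.
- **The AE Grade 3 or higher endpoint ignores censoring.** SAP 5 defines it as "Duration of Avelumab plus Axitinib therapy among patients who discontinued the study drugs due to all-cause AEs" of that grade. Every included patient has an observed time, and SAP 15.1.2 tabulates the corresponding discontinuations separately. It answers a time-to objective only in part, but that is a choice of estimand. Nor can the 7.6% in protocol 7 size it: that figure is treatment-related, while this endpoint is all-cause and Grade 3 or higher.
- **AE duration is the same error.** Protocol 9.7.2 openly limits it: "duration of AE (applicable for resolved AEs only". It describes events, and non-resolution is itself a reported outcome in protocol 9.1.2.2.
- **The whole T2LT gap is bias.** It is not: at 24 months truncation accounts for the smaller part in the base illustration.

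It is also fair that later-line uptake is tabulated separately, so readers will see how many patients received later-line therapy, and that all analyses here are descriptive.

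**Conclusion.** The point holds for T2LT. Followed as written, the plan reports a secondary objective from starters only, with a value that runs short and depends on follow-up. In the base illustration the starters-only median is 1.8-1.9 months with 12 months of follow-up and 2.2-2.4 with 24, against 2.4-2.7 among starters with unlimited follow-up and 3.2-3.4 to 50% cumulative incidence in all discontinuers. These sizes rest on exponential times and on assumed start, death and discontinuation rates that the documents do not supply; the direction does not depend on the values tried.

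A narrower point holds for time to discontinuation. The handling of ongoing patients is unstated in that summary, and entering them at cut-off understates the mean (13.7 against 19.2 months at 24 months) and caps the median at the 12-month analysis, while leaving the 24-month median right when it lies below 24 months.

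The general and specific analysis statements within each document need reconciling. The matter is secondary and should be corrected; it does not touch the primary endpoint.

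**What to change.** In SAP 14.2 and 15.1.1, and in protocol 9.7.3:

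1. Report T2LT as cumulative incidence among all patients who discontinue, with death before second line as a competing event and others censored at last contact. Plain Kaplan-Meier with deaths censored would overstate second-line uptake.
2. Report time to discontinuation by Kaplan-Meier from the index date, with patients still on treatment censored at cut-off.
3. Keep the current summaries as extras, labelled with who is included and how many are not.
4. Reconcile protocol 9.7 with 9.7.3, and SAP 9 with 14.2 and 15.1.1.

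Optionally, add the cumulative incidence of discontinuation due to Grade 3 or higher AEs in all patients, with death and discontinuation for other reasons competing, and show the number of unresolved AEs beside AE duration.

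The cost is wording in both documents and a few tables or curves. Treatment, second-line, death and last-contact dates are already collected or derived.

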15.1 Adverse Events

Treatment-emergent adverse events (TEAEs): those AEs with onset dates occurring within the on-treatment period as defined in [Section 9.8](#).

TEAEs related to study treatment are those events with relationship missing, unknown or related.

Immune-related adverse events (irAE) are identified according to eCRF AE form (“Is this an immune-related event” selected as Yes).

Infusion related reaction (IRR) are identified as per the following table:

Infusion related reactions	
Reactions: considered when onset is on the day of study drugs infusion (during or after the infusion) or the day after the study drugs infusion (irrespective of resolution date):
 
• IRR• Drug hypersensitivity• Hypersensitivity• Type I hypersensitivity• Anaphylactic reaction 
Signs and Symptoms: occurring on the day of study drugs infusion (during or after the infusion) and resolved on the day of onset or the next day:
 
• Pyrexia• Chills• Flushing• Hypotension• Dyspnea• Wheezing• Back pain• Abdominal pain• Urticaria
----------------------------	---

All analyses described in [Section 15.1](#) will be based on TEAEs if not otherwise specified. The AE listings will include all AEs (whether treatment-emergent or not).

Unless otherwise specified, TEAEs will be summarized by number and percentage of participants with the TEAE in the category of interest, primary SOC and PT in decreasing frequency.

Each participant will be counted only once within each SOC or PT. If a participant experiences more than one AE within a SOC or PT for the same summary period, only the AE with the strongest relationship or the worst severity, as appropriate, will be included in the summaries of relationship and severity.

15.1.1 All Adverse Events

The following tables will be presented:

- Overview of TEAEs, summarizing number (%) of patients with any:
 - TEAEs
 - Related TEAEs (overall and to Avelumab or Axitinib)
 - Serious TEAEs
 - Related (overall and to Avelumab or Axitinib) serious TEAEs
 - National Cancer Institute - Common Terminology Criteria for Adverse Events (NCI-CTCAE) (version 5.0) TEAEs Grade ≥ 3
 - Related (overall and to Avelumab or Axitinib) NCI-CTCAE TEAEs Grade ≥ 3
 - TEAEs leading to death
 - Related (overall and to Avelumab or Axitinib) TEAEs leading to death
- Overview of TEAEs leading to discontinuation
- Summary of TEAEs by SOC and PT
- Summary of serious TEAEs by SOC and PT
- Summary of related (overall and to Avelumab or Axitinib) TEAEs by SOC and PT
- Summary of NCI-CTCAE (version 5.0) TEAEs Grade ≥ 3 by SOC and PT
- Summary of TEAEs leading to death by SOC and PT
- Summary of serious related (overall and to Avelumab or Axitinib) TEAEs by SOC and PT
- Summary of serious NCI-CTCAE (version 5.0) TEAEs Grade ≥ 3 by SOC and PT
- Summary of serious TEAEs leading to death by SOC and PT
- Summary of related (overall and to Avelumab or Axitinib) TEAEs NCI-CTCAE (version 5.0) Grade ≥ 3 by SOC and PT
- Summary of related (overall and to Avelumab or Axitinib) TEAEs leading to death by SOC and PT

- Summary of TEAEs NCI-CTCAE (version 5.0) Grade ≥ 3 leading to death by SOC and PT
- Summary of potential signs and symptoms of immune-related TEAEs.

Exposure (exposure duration [days and cycles when applicable] and cumulative dose [milligrams]) among the patients who discontinued the study drugs due to all-cause TEAEs Grade ≥ 3 will be summarized as per appropriate statistics.

Percentage of patients with therapy modifications due to AEs related to Avelumab and/or Axitinib (eg, therapy interruptions and reductions of infusion rate for Avelumab, therapy interruptions and dose reductions for Axitinib) and frequency and type of medical intervention or medications used for the management of related AEs (eg, use of corticosteroids, immunosuppressants, or hormonal therapy) will be presented.

Percentage of patients receiving later-line therapy (eg, second-line therapy, third-line therapy) and frequency distribution of later-line therapy treatments among patients progressing on Avelumab plus Axitinib therapy will be presented.

Time to onset and duration of AEs, time to Avelumab plus Axitinib therapy discontinuation will be summarized by descriptive statistics for continuous variables.

Type of therapy for management of related AEs and type of second-line therapy and third-line therapy will be presented according to the WHO-DD, considering the first digit of the ATC classification system (anatomic category) and the first 3 digits of the ATC class (therapeutic category).

